- if at least 3 patients experience AEs graded as 'moderate' and at least possibly related to the IMP within the same dose level of CLS12311/placebo
- If at least 3 patients (irrespective of the dose group) show an increase of >5 new lesions (CEL or new/enlarging T2) at [REDACTED] compared to the average number of new brain lesions (as defined above) observed during baseline
- if a confirmed relapse (irrespective of the dose group), assessed as severe, occurred within 4 weeks after the last dosing

The DSMB shall give recommendations on the following main outcomes:

- stop further treatment or lower further dosing in individual patients
- stop recruitment and/or treatment or lower dose for a specific treatment arm
- stop recruitment and/or treatment for the clinical trial
- continue the clinical trial as per protocol
- any other trial modification (e.g. additional visits, assessments)

Any recommendation will be explicitly documented in the meeting minutes.

Based on the DSMB recommendations, the Study Steering Committee will decide on actions to be taken as outlined above.

For the DSMB meetings, the DSMB will receive patient listings and statistical summaries, consisting of at least the following in addition to all available data on the patient(s) that made the meeting necessary:

- All patients who experienced SAEs (including relationship and severity)
- All patients who experienced AEs (including relationship and severity)
- All patients who experienced AEs within one day following infusion of CLS12311/placebo including severity and relationship
- All patients who experienced a relapse
- Number of new brain lesions (CEL and new/enlarging T2)
- EDSS scores
- Safety relevant protocol deviations

Detailed requirements on the presentation of listings and summaries and details of the premise and the scope of the DSMB will be specified in the DSMB Charter.

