### 5.2.3 Rationale for the Study Design

CLS12311 is given for the first time in humans, hence the clinical trial is designed to assess safety and tolerability of three dose regimens of CLS12311.

The study will provide data on the safety of a single treatment cycle given in an ascending dose of CLS12311 and will further assess the safety and tolerability of a second treatment in a subset of patients.

Initially, the safety and tolerability of a single treatment cycle of CLS12311 will be assessed in three dose groups in a total of 9 patients. Each dose group will start with a sentinel patient, who will inform about the safety of the treatment in the same dose group. To ensure the safety of dosing in the next patient a time frame of at least four days is defined prior to dosing of the next patient. The definition of this time frame is based on preclinical data showing complete processing of peptide-coupled RBCs in the first 24h after infusion (see IB 5.3). Immediate reaction to the therapy, e.g. hyperacute immune activation and cytokine release or thrombotic events, would be expected in the first hours after treatment. Due to the individual manufacturing of each product and related logistics, only one patient will be treated per week. The treatment will start in the lowest dose groups (2 patients). Further dosing in the higher dose groups (mid dose 3 patients, high dose 4 patients) will be initiated only after safety analysis of the respective prior dose group. During the course of the study the safety and tolerability of a second treatment cycle of CLS12311 will be evaluated in 6 of the 9 patients who received a first treatment cycle. The first patient in each dose group (sentinel patient) will not receive a second treatment cycle of CLS12311, only. Further, patients in each dose group will receive a second treatment in [REDACTED] of the

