#### Single/First treatment cycle

The safety and tolerability of a single treatment cycle of CLS12311 will be assessed in an ascending dose study across three dose groups involving a total of 9 patients. Patients will be allocated to a low (total dose [REDACTED]; n=2), medium (total dose [REDACTED]; n=3) or high dose (total dose [REDACTED]; n=4)

Each dose group will start with a sentinel patient, who will inform about the safety of the treatment before dosing additional patients. To ensure the safety of dosing in the subsequent patient, a minimum time interval of four days will be established prior to dosing the next patient. This time frame is based on preclinical data showing that peptide-coupled RBCs are fully processed in the first 24h after infusion (see IB 5.3). However, due to the individual manufacturing process of each product and related logistics, only one patient will start treatment per week. Patients who fail to meet the eligibility criteria during screening will be replaced.

The treatment will start with the lowest dose group (2 patients). Higher dose groups (medium dose in 3 patients, high dose in 4 patients) will only be initiated once safety data from the preceding dose group, based on (S)AEs and relapses, has been confirmed by Sponsor's medical

expert(s). The corresponding data should be entered into the eCRF in timely manner, within 24 hours at the latest.

The first patient in each dose group (sentinel patient) will receive a single treatment of CLS12311. Sentinel patients will not receive a second treatment cycle. All sentinel patients will be followed with safety visits until Visit 16 (week 48) according to the schedule of visit (see section 4.1). The safety follow-up of sentinel patients will inform about the safety of the treatment prior to second dosing of other patients.

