### Safety Monitoring and DSMB Review

Safety and tolerability will be assessed using vital sign measurements, clinical laboratory tests (hematology, blood chemistry, and urine tests), physical examinations, and monitoring for (S)AEs and relapses.

Twice, after patient 3 and then after patient 6 have completed [REDACTED], the Sponsor's medical expert(s) will review safety data, including any serious and severe events judged to be related to peptide-coupled RBCs, to confirm safety of repeated dosing for patient 2 and for patients 4 and 5, respectively.

To ensure availability of safety data a stringent enrollment of patients has been defined (Figure 7-1).

Patients 1, 2 and 3 will be enrolled to receive a dose of [REDACTED] of peptide-coupled RBCs (patients 1 and 2) or [REDACTED] (patient 3) in the first treatment cycle (see 10.2.1). Only after confirmation of the tolerability and safety of the first treatment cycle in **patient 3** (single dose of [REDACTED]) at safety assessments visit in [REDACTED], the second treatment cycle of patient 2 (total cumulative dose of [REDACTED]) will be permitted.

Accordingly, patients 4, 5 and 6 will be enrolled [REDACTED]. Patients 4 and 5 will only receive the second treatment cycle (total cumulative dose of [REDACTED]) if the [REDACTED] safety data of **patient 6** (single dose of [REDACTED]) will support second dosing of CLS12311.

The second treatment cycle of the last three patients (patients 7 - 9) will be administered only after the safety and tolerability of second treatment cycle has been confirmed in **patients 4 or 5**. If safety data of [REDACTED] from patients 3 or 6 are not available due to prematurely discontinuation, second dosing of patient 2, 4 or 5 need to be postponed until sentinel patients are replaced and safety data are available.

After the last patient in the high dose group has completed [REDACTED] safety data (including MRI data, relapses and EDSS) of all patients will be evaluated by the DSMB.

[figure not shown]

If any of the treatment regimens are deemed to be unsafe, the DSMB may recommend protocol modifications or omit any of the dose levels (see Section 19.1.3). A substantial change will be submitted for approval by IRBs/ECs and the regulatory authorities, in accordance with CTR and Swiss ClinO (see Section 19.7).

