**Figure 7-1    Patients’ enrollment and safety assessments in the treatment phase**

## 7.2 Safety Follow Up Phase: approx. 31 weeks

At the completion of the treatment phase, patients will enter a 31-week safety follow up (SFU) period, including three visits: three weeks after the end of the treatment period (Week 20), at Week 24 and at Week 48.

During the SFU, patients will be assessed at clinical visits as per Schedule of Events – please refer to Table 4.1 for further details.

The DSMB will reconvene after the completion of [REDACTED] to assess the safety outcomes of the trial.

[figure not shown]
If patients wish to discontinue the unblinded SFU and the last visit has been more than 8 weeks ago, they should be invited for an ED visit to capture safety data and ensure continued patient monitoring.

As the duration of the treatment effect is not known, patients may begin another DMT during the SFU, at the discretion of the investigator. However, every effort should be made to have patients complete the SFU and all related assessments, regardless of whether or not they receive alternative treatment for their MS.

In summary, this Phase Ib trial is designed to provide a maximum of safety throughout both single dose escalation and second treatment cycle.

Safety data will be evaluated by a DSMB after key milestones to assess the overall safety of CLS12311 and the different dose levels tested. A brief overview of the course of the Phase Ib study is shown in Figure 7-2.

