### 9.3.1 Discontinuation Criteria Related to the Study

The study can be terminated by the Sponsor Cellerys at any time.

The criteria for early discontinuation / termination of the clinical trial include (not exclusively):

- An unexpected, significant, or unacceptable safety risk to participants enrolled in the study.
- A decision based on recommendation from applicable boards after review of safety data. A DSMB will be implemented to assess safety to provide rationale for discontinuation of the study (section 19.1.3).
- Patients cannot be recruited in sufficient numbers.

In the decision to terminate, Cellerys will always consider participants' welfare and safety. Should early termination be necessary, participants must be seen as soon as possible as described in section 14.1.9.

The Investigator may receive additional procedures to ensure that adequate consideration is given to the protection of the participant's interests. The Investigator or Sponsor depending on local regulation will be responsible for informing IRBs/IECs of the early termination of the trial.

For every patient who prematurely discontinues the trial prior to Visit 3 (dose group 1) or Visit 4 (dose groups 2 and 3), an additional patient will be included. Every sentinel patient who discontinues the trial prior to [REDACTED] has to be replaced. In the mid dose group, safety data of the second treatment cycle should be available from at least one patient (patient 4 or 5).. Any patient with insufficient safety information may be replaced at the discretion of the Sponsor, to maintain the safety integrity of the dose escalation schedule.

For participants who choose to withdraw from the study, all data collected up to the point of withdrawal will be securely stored and analyzed per protocol.

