##### **19.1.3 Data Safety Monitoring Board (DSMB)**

A Data and Safety Monitoring Board (DSMB) consisting of at least 3 independent MS- and trial experts will be chartered to review the safety of the trial. Beside tolerability and safety of CLS12311, the DSMB will also evaluate signs of worsening of MS assessed by new lesions on brain MRI and occurrence of relapses and disability progression based on EDSS.

After both patients in the low dose group and all three patients in the medium dose group have completed [REDACTED], the Sponsor's medical expert(s) will decide based on (S)AEs and relapses, whether the next dose level of the treatment can be applied.

As soon the last patient in the high dose group has completed [REDACTED] safety data (including MRI data, relapses and EDSS) of all patients will be evaluated by the DSMB. Finally, after the last patient in the high dose group has completed [REDACTED] the DSMB will meet again to evaluate safety of the 12-week follow-up after the second treatment cycle in all patients.

The DSMB shall give recommendations on the following main outcomes:

- stop further treatment or lower further dosing of individual patients
- stop recruitment and/or treatment or lower dose for a specific dose group
- stop recruitment and/or treatment for the clinical trial
- continue the clinical trial as per protocol
- any other trial modification (e.g. additional visits, assessments)

Any recommendation will be explicitly documented in the meeting minutes.

Based on the DSMB recommendations, the Study Steering Committee, consisting of the Sponsor and selected country Investigators, will decide on actions to be taken as outlined above.

For the DSMB meetings, the DSMB will receive patient listings and statistical summaries, consisting of at least the following in addition to all available data on the patient(s) that made the meeting necessary:

- All patients who experienced SAEs (including relationship and severity)
- All patients who experienced AEs (including relationship and severity)
- All patients who experienced AEs within one day following infusion of CLS12311/placebo including severity and relationship
- All patients who experienced a relapse
- Number of new brain lesions (CEL and new/enlarging T2)
- EDSS scores
- Safety relevant protocol deviations

Detailed requirements on the presentation of listings and summaries, as well as details of the premise and the scope of the DSMB, will be specified in the DSMB Charter.

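### Read by dose group, the moderate-AE trigger for a DSMB meeting (at least 3 patients at one dose level) cannot be met in the planned two-patient low-dose group; the new/enlarging T2 part of the lesion trigger also has no Visit 1 value.

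*Protocol*

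**What the plan says.** **Moderate-AE trigger.** The synopsis (Protocol section 3, Data and Safety Monitoring) lists four events that require an unscheduled DSMB meeting. One applies "if at least 3 patients experience AEs graded as 'moderate' and at least possibly related to the IMP within the same dose level" of CLS12311/placebo. A parallel trigger for severe related AEs needs one patient. The lesion and severe-relapse triggers are stated to apply whatever the dose group; the two AE triggers carry no such words.

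**Group sizes.** Section 5.2.3: "The treatment will start in the lowest dose groups (2 patients". Section 7.1: "Higher dose groups (medium dose in 3 patients, high dose in 4 patients) will only be initiated once safety data from the preceding dose group" has been confirmed.

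**The term *dose level*.** It has no formal definition in either document. Section 7.1 says "the DSMB may recommend protocol modifications or omit any of the dose levels". Section 7.2 has the DSMB evaluate data "to assess the overall safety of CLS12311 and the different dose levels tested". Section 19.1.3 says that, once the low-dose and then the medium-dose patients have reached a set point, the sponsor's medical experts "will decide based on (S)AEs and relapses, whether the next dose level of the treatment can be applied".

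**Replacement.** Section 9.3.1 requires replacement of sentinels who leave early and adds: "Any patient with insufficient safety information may be replaced at the discretion of the Sponsor".

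**Lesion trigger.** It is met when at least 3 patients, in any group, show an increase of more than 5 new lesions (CEL or new/enlarging T2) "compared to the average number of new brain lesions (as defined above) observed during baseline". Section 14.1.1 and the schedule give one baseline MRI. SAP 5.5.3 counts new/enlarging T2 lesions against the previous scan and defines the MRI baseline as the Visit 1 CEL count only.

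**The concern.** This is a first-in-human escalation, and section 7.1 counts the DSMB triggers among the key measures protecting participants. Escalation is decided by the sponsor's experts. The first scheduled DSMB meeting comes only after the last high-dose patient has reached a set point (synopsis, Safety analysis timepoints). Until then, the triggers are the only stated rule that obliges the independent board to meet. A threshold of 3 patients in a group of 2 does nothing at the dose where the product is first given to humans. In the medium group it acts only when every patient is affected.

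The lesion trigger raises a smaller question. Section 13.4.5 relies on MRI as the sensitive measure of disease exacerbation, yet part of that trigger compares against a quantity that is not measured at baseline. Section 13.4.5 also sends the reader to 19.1.3 for the trigger rules, and 19.1.3 does not list them.

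**Working it through.** **Plan's own total.** 2 + 3 + 4 = 9, which agrees with the planned enrolment. The plan gives no operating characteristics for the triggers, so there is nothing further to reproduce.

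**Counts on the dose-group reading, with no assumed risk.** Section 10.2.1 numbers the patients: low = 1 and 2, medium = 3 to 5, high = 6 to 9.

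- At least 3 per group: no group has a third patient until patient 5, so patients 1 to 4 could all be affected without meeting the rule. The largest number affected without meeting it is 2 + 2 + 2 = 6 of 9.
- At least 2 per group: the rule can be met from patient 2. The largest number affected without meeting it is 1 + 1 + 1 = 3 of 9.

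**Chance of meeting the rule.** The documents give no per-patient risk p of a moderate related AE, so 10%, 30% and 50% are assumptions. Patients are treated as independent, X ~ Binomial(n, p). Example for n = 4, p = 0.3: P(X ≥ 3) = 4 × 0.3³ × 0.7 + 0.3⁴ = 0.0756 + 0.0081 = 0.0837. *Any group* is 1 minus the product of the three values of (1 − P).

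| Assumed p | Rule | Low, n = 2 | Medium, n = 3 | High, n = 4 | Any group |
|---|---|---|---|---|---|
| 10% | ≥ 3 | 0 | 0.001 | 0.0037 | 0.005 |
| 10% | ≥ 2 | 0.01 | 0.028 | 0.0523 | 0.088 |
| 30% | ≥ 3 | 0 | 0.027 | 0.0837 | 0.108 |
| 30% | ≥ 2 | 0.09 | 0.216 | 0.3483 | 0.535 |
| 50% | ≥ 3 | 0 | 0.125 | 0.3125 | 0.398 |
| 50% | ≥ 2 | 0.25 | 0.50 | 0.6875 | 0.883 |

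The low-dose entry for the present rule is 0 at every p, including p = 1.

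**Extra meetings from a threshold of 2.** Sum of P(X ≥ 2) minus sum of P(X ≥ 3) over the groups:

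- 10%: 0.0903 − 0.0047 = 0.086
- 30%: 0.6543 − 0.1107 = 0.544
- 50%: 1.4375 − 0.4375 = 1.0

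**Alternative reading.** If *dose level* means the dose infused on the first infusion day, groups 1 and 2 both receive one coupled and one placebo bag (synopsis, Dosing), so 2 + 3 = 5 patients share a level. P(X ≥ 3) with n = 5 is then 0.0086, 0.1631 and 0.5000 at the three assumed risks.

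**Lesion trigger.** With one baseline scan, the baseline average is a single value. For CEL that value exists and the comparison can be made. For new/enlarging T2, the first count arises at the second scan, because it is defined against an earlier one; the SAP 5.5.3 collection table is accordingly empty in its first column for that row. There is nothing at Visit 1 to subtract.

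**The case against.** The strongest reply is that *dose level* is undefined, so what is shown is an ambiguity. The AE triggers speak of a dose level of CLS12311 or placebo, while the next two say dose group. No group is placebo-only, so the wording could refer to an infusion, and pooling groups 1 and 2 would make 3 reachable. This stands as a caveat. The usage in 7.1, 7.2 and 19.1.3, and the fact that only the lesion and relapse triggers are released from the dose group, still favour the dose-group reading.

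A reader might infer that six patients could have moderate related AEs with no DSMB involvement at all. The documents do not support that. One related severe AE, or one confirmed severe relapse within 4 weeks of dosing, calls the board in any group. Reviews after each patient are done by the sponsor's experts and/or the DSMB. Section 14.5 has rules for withholding further infusions, and the scheduled DSMB meetings take place regardless. Replacing a dosed low-dose patient under 9.3.1 could also supply a third.

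It can also be said that keeping the board for clusters of moderate events, with one severe event sufficient, is a legitimate choice. It is, and no document dictates 2. But a number that exceeds the size of a planned group looks unintended; if it was meant, the protocol should say so.

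On MRI, a reader might infer that the lesion trigger as a whole cannot be evaluated. That is too strong: the CEL part works, and new/enlarging T2 is already a change count that needs no subtraction. What remains is wording.

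**Conclusion.** The point holds, conditionally. On the better-supported reading and with planned numbers, this trigger cannot be met in the low-dose group at any event rate, needs 3 of 3 in the medium group and 3 of 4 in the high group, and could go unmet with 6 of 9 patients affected. Those counts need no assumed risk. The probabilities rest on assumed risks and independence and only illustrate the difference between thresholds. The gap is partial because the other safeguards operate, so this is worth correcting but does not show the escalation to be unsupervised. The T2 comparator is a real but secondary defect of wording. Confidence is medium: the term is undefined, and the DSMB Charter and MRI manual, which were not available, may already resolve both points.

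**What to change.** 1. Define *dose level* as dose group and set the moderate-AE trigger at a number attainable in every planned group, for example at least 2 patients. The final value is for the sponsor and the DSMB.
2. Keep the lesion trigger at 3 patients in any group, and restate the per-patient criterion: more than 5 CEL above the patient's own Visit 1 CEL count, or more than 5 new/enlarging T2 lesions accumulated since the Visit 1 scan, with no baseline subtraction. Counts from any unscheduled MRI in between should be added; otherwise a relapse scan (14.1.8) becomes the previous MRI and splits the count. Note that the interval from Visit 1 to first dosing varies (15.1), so some counted lesions may predate dosing.
3. List the triggers in 19.1.3, and align the DSMB Charter and MRI manual.
4. The SAP revision history records an update after a data review in January 2026, so dosing may be complete. If so, state in the study report, labelled post hoc, whether the restated triggers would have been met. The AE and MRI listings already planned in the SAP supply the data.

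The cost is wording in the protocol and charter, or one short report statement. With a threshold of 2, the downside is at most one extra ad hoc DSMB meeting per dose group.

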## 4 SCHEDULE OF EVENTS AND TREATMENT

### 4.1 Part A

Visit																UV
																Unscheduled 
Week																
Study Phase	BL	Treatment												SFU		
Informed consent	x															
Eligibility criteria	x	x														
Body weight, height	x															
ECG	x															
Medical history including MS history  / Demography/ Smoking history/ Prior medication/ SARS-CoV-2 vaccination status	x															
Physical examination	x					x	x						x		x	x
Vital signs	x	x	x	x		x	x		x	x	x		x		x	x
Urine pregnancy test 	x	x	x	x			x		x	x	x		x		x	x
HLA typing 	x															
Cranial MRI	x 						x 						x 		x 	x 
Hematology  / Blood biochemistry 	x						x						x		x	x
Urinalysis 	x						x						x		x	x
Infectious disease screen 	x															
EDSS	x						x						x		x	x
9-HPT, T25-FW, SDMT	x						x						x		x	x
Eligibility for blood donation 																
Blood donation																

Visit																	UV
																	Unscheduled 
Week																	
Study Phase	BL	Treatment												SFU			
CLS12311/ (Placebo) 																	
Concomitant medication/procedures		x	x	x	x	x	x	x	x	x	x	x	x	x	x	x	x
MS relapse assessment		x	x	x		x	x		x	x	x		x		x	x	x
Adverse event assessment	x	x	x	x	x	x	x	x	x	x	x	x	x	x	x	x	x
Telephone-based AE assessment the next day following infusion 			x	x						x	x						
Antigen specificity 	x						x						x				
Biomarker blood	x						x						x				

MS Multiple Sclerosis; MRI Magnetic Resonance Imaging; EDSS Expanded Disability Status Scale (neurological rating scale); 9-HPT Nine Hole Peg Test (clinical test for hand function); T25-FW Timed 25-Foot Walk; SDMT Symbol Digit Modalities Test (cognitive test); ECG electrocardiogram; BL Baseline; EOT End of Treatment; EOS End of Study; ED Early Discontinuation; SFU Safety Follow Up; HLA Human Leukocyte Antigen

 MS history means first MS symptoms and diagnosis, prior relapses, prior disease modifying therapies and symptomatic therapies.

 Only in female patients of childbearing potential (sexually mature, premenopausal and not surgically sterile). To be performed locally.

